12.1.4 Suspected Unexpected Serious Adverse Reaction (SUSAR)

A SUSAR is a suspected, unexpected serious, adverse reaction that is deemed related to IMP, where the nature of the adverse event or severity of the event is not consistent with the applicable product information (e.g. reference safety information). All AEs and SAEs will be assessed by CDD for seriousness, causality and expectedness. The Pharmacovigilance Department will expedite all SUSARs to the relevant Competent Authority/Authorities and the relevant Ethics Committee(s) within the timelines specified in legislation (SI 2004/1031 as amended).

12.1.5 Urgent Safety Measures (USM)

The Sponsor or Investigator may take appropriate USMs in order to protect the patient of a clinical trial against any immediate hazard to their health or safety. This includes procedures taken to protect patients from pandemics or infections that pose serious risk to human health.

USMs may be taken without prior authorisation from the competent authority. However, The Medicines and Healthcare products Regulations Agency (MHRA) and the Research Ethics Committee (REC) must be notified within three days of such measures being taken.

Should the site initiate a USM, the Investigator must inform the Sponsor immediately either by:

The notification must include the minimum information:

- the date of the USM;
- who took the decision;
- what action has been taken and
- why the action was taken.

The Sponsor will then notify the MHRA and the REC within three days of USM initiation.

12.2 Causality

The relationship of each adverse event to the trial medication must be determined by a medically qualified individual according to the following definitions:

Highly probable	Starts within a time related to the IMP administration and No obvious alternative medical explanation.
Probable	Starts within a time related to the IMP administration and Cannot be reasonably explained by known characteristics of the patient's clinical state.
Possible	Starts within a time related to the IMP administration and A causal relationship between the IMP and the AE is at least a reasonable possibility.
Unlikely	The time association or the patient's clinical state is such that the trial drug is not likely to have had an association with the observed effect.

Not related	The AE is definitely not associated with the IMP administered.
-------------	--

Note: Drug-related refers to events assessed as possible, probable or highly probable.

The Investigator must endeavour to obtain sufficient information to determine the causality of the AE (i.e. IMP, other illness etc.) and must provide his/her opinion of the causal relationship between each AE and IMP. This may require instituting supplementary investigations of significant AEs based on their clinical judgement of the likely causative factors and/or include seeking a further opinion from a specialist in the field of the AE.

The following guidance should be taken into account when assessing the causality of an AE:

- Previous experience with the IMP and whether the AE is known to have occurred with the IMP.
- Alternative explanations for the AE such as concomitant medications, concurrent illness, non-medicinal therapies, diagnostic tests, procedures or other confounding effects.
- Timing of the events between administration of the IMP and the AE.
- IMP blood levels and evidence, if any, of overdose.
- De-challenge, that is, if the IMP was discontinued or the dosage reduced, what happened to the adverse reaction?
- Re-challenge, that is, what happened if the IMP was restarted after the AE had resolved?

12.3 Procedures for Recording Adverse Events

All AEs will be recorded in the eCRF.

The following information will be recorded: patient ID including the patient trial number, age and gender; verbatim term for the AE description, date of onset and end date as well as outcome, severity of the event, assessment of relatedness to trial medication, other suspect drug or device and action taken. Follow-up information should be provided as necessary. AEs should be recorded on the CRF from the date of written/verbal informed consent (whichever is the earlier) being given until they have completed the 28 days from Day 1 follow up period.

AEs considered related to the trial medication or COVID-19, as judged by a medically qualified investigator or the sponsor will be followed until resolution or the event is considered stable. All related AEs that result in a patient's withdrawal from the trial or are present at the end of the trial, should be followed up until a satisfactory resolution occurs.

It will be left to the investigator's clinical judgment whether or not an AE is of sufficient severity to require the patient's removal from treatment. Although the Sponsor will hold the final decision if there is a disagreement in the management of the patient's treatment. A patient may also voluntarily withdraw from treatment due to what he or she perceives as an intolerable AE. If either of these occurs, the patient must undergo an end of study assessment and be given appropriate care under medical supervision until symptoms of the AEs cease or the condition becomes stable.

The severity of events will be assessed on the following scale: 1 = mild, 2 = moderate, 3 = severe and as judged by a medically qualified investigator.

For hospitalised patients who are admitted (for any reason other than COVID-19) and subsequently test positive for COVID-19, medical occurrences or symptoms of deterioration that are expected as a consequence of the participant's admission hospital should be recorded in the patient's medical notes and only be reported as AEs in the eCRF if medically judged to have unexpectedly worsened during the study. AEs considered related to the trial medication or COVID-19, as judged by a medically qualified investigator or the sponsor will be reported in the eCRF.

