2 SYNOPSIS

Study Title	A Randomised Phase II trial in early COVID-19, assessing use of camostat by blocking SARS-CoV-2 Spike protein-initiated membrane fusion.
Short title	SPIKE-1
Sponsor	Cancer Research UK
Funder	LifeArc
Trial Design	
A randomised, multicentre, prospective, open label, community-based clinical trial.
 
There are two arms:
 
Treatment arm: Patient to receive treatment with camostat tablets, 200mg four times daily (qds) for 14 days
 
Control arm (non-treatment): Patient to receive best supportive care.
 
Patients will be randomised 1:1 into each of these arms until both arms have recruited up to 50 patients.
 
Early assessment of recruitment and trial feasibility will be critical therefore the Trial Management Group (TMG) will provide ongoing review of these aspects and propose modification for regulatory/ethical approval as appropriate.

Trial patients	
 ▪ Adults, 18 years of age and above ▪ Symptomatic COVID-19 infection ▪ Evidence of current COVID-19 infection from a validated assay 
Patients will be recruited through various methods including but not limited to:
 
 • General Practitioner (GP) practices • Advertisement (e.g. on social media, at testing centres) • COVID hubs • Identification through other hospital departments (e.g. Emergency Departments, Acute Assessment Units, Oncology etc.) • NHS Digital • Hospital in-patients • Test and Trace, or equivalent
Sample size	Up to 100 patients (randomised 1:1 treatment and control arm).
Planned trial period	Start date August 2020. The anticipated end date for this trial is July 2021, however that may be amended based on emerging data and circumstances.
Planned recruitment period	Approximately 12 months
Primary Objective and Endpoint	
Objective	Endpoint
To further assess the safety and toxicity profile of camostat. to support integration into a Phase III trial.	Causality and severity of each adverse event (AE) to camostat.
Secondary Objectives and Endpoints	

To confirm that the PK profile aligns with the established PK profile for the active metabolite of camostat, 4-(4-guanidinobenzoyloxy) phenyl acetic acid (GBPA).	Confirm PK parameters of GBPA as assessed by population estimates from population PK analysis (popPK).

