12 SAFETY REPORTING

12.1 Definitions

12.1.1 Adverse Event (AE)

An AE or adverse experience is:

An adverse event (AE) is any untoward, undesired or unplanned medical occurrence in a patient administered an investigational medicinal product (IMP), a comparator product or an approved drug.

An AE can therefore be any unfavourable and unintended sign (including an abnormal laboratory finding), symptom or disease temporally associated with the use of the trial medication, whether or not considered related to the trial medication.

AEs should be reported for all patients regardless of which arm they were randomised to.

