12.1.3 Serious Adverse Event (SAE)

A serious adverse event is any untoward medical occurrence that at any dose:

- Results in death
- Is life-threatening, NOTE: A "life-threatening" event is defined as an event when the patient was at substantial risk of dying at the time of the AE occurring; it does not refer to an event which hypothetically might have caused death if it were more severe.
- Requires in-patient hospitalisation where they are admitted for more than 24 hours or prolongs existing in-patient hospitalisation (although some hospitalisations are exempt from SAE reporting, i.e. hospital admissions planned prior to the patient entering the trial; overnight stays for planned procedures). NOTE: if a patient is in hospital when they sign informed consent to participate in the trial, any event after consent that would have resulted in hospitalisation, or any event that prolongs the existing in-patient hospitalisation should be reported as serious.
- Results in persistent or significant disability/incapacity, or
- Is a congenital anomaly/birth defect.
- Other important medical events. NOTE: A medically important event is defined as any event that may jeopardise the patient or may require intervention to prevent one of the outcomes listed above. Examples include allergic bronchospasm (a serious problem with breathing) requiring treatment in an emergency room, serious blood dyscrasias (blood disorders) or seizures/convulsions that do not result in hospitalisation. Development of drug dependency or drug abuse including overdose would also be examples of important medical events. Other events that may not result in death, are not life threatening, or do not require hospitalisation, may be considered a serious adverse event when, based upon appropriate medical judgement, the event may jeopardise the patient and may require medical or surgical intervention to prevent one of the outcomes listed above.

To ensure no confusion or misunderstanding of the difference between the terms "serious" and "severe", which are not synonymous, the following note of clarification is provided:

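### In hospital-recruited patients, the section 12.3 exemption lets adverse event ascertainment differ by arm, with size and net direction unknown

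*Protocol*

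**What the plan says.** Protocol section 12.3 opens with a general rule: "All AEs will be recorded in the eCRF". Section 12.1.1 adds that "AEs should be reported for all patients regardless of which arm they were randomised to".

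The last paragraph of 12.3 makes an exception for patients admitted for a reason other than COVID-19 who then test positive. Events expected from that admission go in the medical notes and should "only be reported as AEs in the eCRF if medically judged to have unexpectedly worsened during the study". A second route follows: "AEs considered related to the trial medication or COVID-19, as judged by a medically qualified investigator or the sponsor will be reported in the eCRF".

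Three other provisions determine how this works in practice:

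- The comparator is untreated. The synopsis describes it as "Control arm (non-treatment): Patient to receive best supportive care", and section 5.1 describes the trial as open label.
- In section 12.2 the three grades that count as drug-related (possible, probable, highly probable) each carry the condition "Starts within a time related to the IMP administration".
- For patients already in hospital at consent, section 12.1.3 says that "any event that prolongs the existing in-patient hospitalisation should be reported as serious". Section 12.5 requires all SAEs to be reported whatever their cause.

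On the analysis side, section 12 of the SAP appendix names the between-arm comparison of adverse events and their severity as the primary outcome. SAP section 6.7 tabulates all AEs and treatment-emergent AEs by arm.

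**The concern.** An admission-expected event in a camostat in-patient has three ways onto the eCRF: unexpected worsening, relatedness to COVID-19 and relatedness to the drug. The same event in a control in-patient has two, because nobody can attribute it to a drug that was not given. Staff who know the allocation decide whether the third route applies. Section 12.2 also asks them to weigh whether the event is already known with camostat, which draws attention to the events of interest in section 12.6, such as nausea.

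What is at stake is comparability of the AE counts between arms in this subset. Reporting the difference without a significance test does not protect it, since a descriptive difference is distorted just as much by unequal recording. Analysis cannot repair it either, because events left in the notes never enter the database. Recruitment setting is not a randomisation stratum (introduction to the SAP appendix), nor a planned subgroup (Protocol 13.1, SAP appendix 11.4), so the planned tables would not show the problem.

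**Working it through.** **The plan's own figures.** None bears on this point. The one stated design figure, the precision of a 50% recruitment rate (Protocol 13.2), reproduces with 200 approached: √(0.25/200) = 3.5%, giving 43% to 57%. It says nothing about AE recording. The documents give neither the number of hospital recruits nor AE rates, so every input below is an assumption chosen to show direction and range.

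**Inputs**

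- h = hospital recruits per arm: 5, 10 or 25 of 50
- λ = admission-expected events per patient: 2
- w = share that worsens unexpectedly: 10%
- c = share judged COVID-19 related: 20% in both arms
- m = share of the remainder judged at least possibly related to camostat: 10% or 30%; 0 in control
- d = true proportional excess on camostat: 0, 25% or 50%; 0 in control

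**Formula.** Recorded events = h × λ × (1 + d) × [1 − (1 − w)(1 − c)(1 − m)].

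The recorded fraction in control is 1 − 0.9 × 0.8 = 0.28. On camostat it is 1 − 0.72 × 0.9 = 0.352 at m = 10%, and 1 − 0.72 × 0.7 = 0.496 at m = 30%. All are below 1, so both arms lose events and control loses a larger share.

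**No drug effect (d = 0).** With h = 10, each arm has 20 true events. Control records 5.6. Camostat records 7.0 (m = 10%) or 9.9 (m = 30%).

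| h per arm | Spurious excess, m = 10% | Spurious excess, m = 30% |
|---|---|---|
| 5 | 0.7 events | 2.2 events |
| 10 | 1.4 | 4.3 |
| 25 | 3.6 | 10.8 |

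For patients with at least one such recorded event, take Poisson counts. The control proportion is 1 − exp(−0.56) = 0.429. On camostat it is 1 − exp(−0.704) = 0.505 or 1 − exp(−0.992) = 0.629. Multiplying the difference by h/50 gives 0.8 points (h = 5, m = 10%) to 10.0 points (h = 25, m = 30%) of a 50-patient arm. This counts only admission-expected events. It would move the any-AE rate by less where the same patients already have another recorded AE.

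**True drug effect, h = 10**

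| True excess | Recorded excess, m = 10% | Recorded excess, m = 30% |
|---|---|---|
| 5.0 events (d = 25%) | 3.2 | 6.8 |
| 10.0 events (d = 50%) | 5.0 | 9.3 |

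At d = 25% the rule understates harm by 1.8 events or overstates it by 1.8, depending on m. At d = 50% it understates harm in both columns.

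**Unequal COVID-19 attribution, h = 10, d = 0, m = 30%.** Suppose assessors attribute ambiguous control events to COVID-19 more often. At 44% in control against 20% on camostat, the control fraction is 1 − 0.9 × 0.56 = 0.496, the same as on camostat, and the spurious difference is 0. At 50% it reverses, to −1.1 events.

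**One arm-neutral rule.** If every such event is recorded in both arms, the recorded fraction is 1 in each and the difference due to this filter is 0.

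**The case against.** The strongest case on the other side is that the exception is worded identically for both arms, covers a subset of a trial that the synopsis calls community-based, and leads only to descriptive tables. Section 4 of the Protocol defines the primary endpoint as causality and severity of AEs to camostat, and the rule expressly keeps events judged drug-related. A general rule followed by a specific exception is also ordinary drafting. The limits on scope and consequence are fair. Identical wording does not make the rule neutral, however, when one of its conditions can be met in only one arm.

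Four stronger readings are tempting, and the documents do not support them:

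- *A reader might infer that AE counts are inflated against camostat.* The filter only removes events, so it raises no count above its true number, and the working shows that the sign of the bias is not fixed.
- *A reader might assume that no control event is recorded.* Suppose 40% of in-patients have an expected event and half of those on camostat are rated possible. That gives 20% against 0%, or 2 to 8 points of the arm if in-patients make up 10% to 40% of it. This closes the worsening and COVID-19 routes, which stay open to control, and the in-patient share has no source in the documents. It is a worst case.
- *A reader might infer that serious events are lost.* Sections 12.1.3 and 12.5 keep them reportable whatever the cause, and many events that prolong a stay will also count as unexpected worsening. A narrow gap remains. An expected, non-worsened event that still prolongs the stay goes to Pharmacovigilance on its own form, yet 12.3 could keep it off the eCRF and so out of the SAP's SAE table.
- *A reader might infer that the laboratory events of interest vanish.* Potassium, liver enzymes and platelets are scheduled on Days 7 and 14 for all patients (8.3.2), although sampling can be waived, and results are listed per patient (SAP 6.8) whether or not an AE is entered. Symptom events such as nausea are more exposed.

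**Conclusion.** The point holds in a limited form. Section 12.3 permits differential ascertainment of adverse events by arm among hospital-recruited patients, through a relatedness judgement made with the arm known. It mainly affects non-serious events in the all-AE and treatment-emergent AE tables by arm. Tables restricted to camostat-related events are one-armed by nature and are not the issue.

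If camostat has no effect on these events and COVID-19 attribution is equal between arms, the rule would show an excess on camostat that is not there. If real drug events are dismissed as expected from the admission, it would hide harm. The net direction and size cannot be settled from the documents. The figures in the working (0.7 to 10.8 spurious events with no drug effect, and a bias of either sign otherwise) rest wholly on assumed inputs and show only that the effect need not be trivial in arms of 50. The correction is cheap and worth making, but this is not a flaw that undermines the trial as a whole.

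**What to change.** 1. Reconcile the exception with the opening rule of section 12.3. Record the adverse events of hospital-recruited patients in the eCRF in both arms under one rule that does not depend on allocation.
2. Add a yes/no eCRF field, *expected consequence of the admission condition*. Use it to describe events, never to decide whether an event is recorded.
3. In the SAP, tabulate AEs by arm and recruitment setting, with and without flagged events.
4. State in 12.3 that no event that is serious under 12.1.3 is kept off the eCRF as expected from the admission. Keep that section's own exemptions for planned admissions and planned overnight stays.
5. For in-patients already enrolled when the rule changes, abstract earlier events from the notes or report those patients separately, so that two recording rules are not mixed in one table.

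The cost is a wording change, one data field, modest extra AE entry for the in-patient subset and, if the change is made mid-trial, some note abstraction.

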12.4 Procedures for recording pregnancies

Any pregnancy occurring during the clinical trial (within 28 days after the last dose of camostat) and the outcome of the pregnancy (including the partner of a male patient), should be recorded using a pregnancy notification form and followed up until 6 months post a known outcome. If the outcome of the pregnancy results in an SAE such as congenital abnormality or birth defect, an SAE should be reported in accordance with Section 12.5.

The Investigator should document within the patient notes, the patient confirming consent for the Sponsor to collect pregnancy follow-up information. In the case that the partner of a patient becomes pregnant, a consent form should be provided to the patient's partner in order to obtain consent for collecting privacy data, in accordance with data protection regulation.

If a pregnancy is confirmed (for a female trial patient) whilst on the trial, the patient must be withdrawn from trial treatment.

12.5 Reporting Procedures for Serious Adverse Events

For eligible patients, SAE collection and monitoring (as per risk assessed monitoring plan) will commence at the time the patient gives their written/verbal consent (whichever is the earlier) to participate in the trial and will continue for 28 days from Day 1.

In addition to the SAE reporting criteria in Section 12.1.3,

During the trial period (Days 1-28):

- All hospitalisations as per the definition stated in Section 12.1.3 (regardless of causality) will be followed up until resolution, discharge or death.
- Patients who are hospitalised will also be followed up, up to 28 days after they are discharged.

Following the trial period, up to the Day 28, only SAEs related to camostat are reportable. These will be followed up until resolution, discharge or death.

Should an Investigator become aware of any IMP-related SAEs after this period, these must also be reported to the CDD within the expedited timelines.

All SAEs regardless of causality must be reported to the Pharmacovigilance Department within 24 hours of becoming aware of the event. SAEs should be documented on an SAE report form, using the completion guidelines provided. SAE report forms should be emailed to the Pharmacovigilance Department mailbox: [REDACTED] The following information must be provided as a minimum:

- Patient identifiers including patient trial number and initials, age or date of birth and gender,
- SAE term, onset date and causality assessment
- A description of the SAEs
- Dose and duration of the treatment with the medicine
- The batch number of the medicine
- Any other medications being taken at the same time including non-prescriptive medicines, herbal remedies and contraceptives
- Any other health conditions the patient has or may have

Follow-up of SAEs by the Pharmacovigilance Department will continue until the events resolve or stabilise. The Pharmacovigilance Department will make requests for further information on SAEs to the Investigators at regular intervals. Requested follow-up information should be reported to the

Pharmacovigilance Department in a timely manner and as soon as possible after receipt of the follow-up request or within 24 hours of becoming aware of new/updated information.

12.6 Specific Events of Interest

The following events will be closely monitored as trial specific events of interest:

- Shock or anaphylactoid symptoms such as decreased blood pressure, dyspnoea and pruritis
- Rash, pruritis
- Gastrointestinal events (nausea, abdominal discomfort, abdominal distension)
- Changes in liver enzymes (AST, ALT, GGT) or jaundice
- Thrombocytopenia
- Hyperkalaemia

